Multiple reports are available on SBRT for lung tumors. In several series reporting both primary and metastatic lung tumors treated with SBRT (with 3-5 fractions), local control rates have been impressive, ranging from 70% to 90% (34,42,43). Furthermore, toxicity has been mild, most commonly limited to radiographic lung changes. A phase I dose-escalation trial was performed for patients with lung metastases from various primary sites. SBRT dose was successfully escalated to 60 Gy in three fractions with minimal toxicity reported (21). A case series reported 50 patients with lung metastases who were treated at University of Rochester, most of whom (62%) received 5 Gy/fraction for a total of 50 Gy. Up to five targets were treated per patient. With a mean follow-up of 18.7 months local control of treated lesions was obtained in 42 of 49 evaluable patients (83%). Only 2% had grade 3 toxicity (22). Investigators from Japan reported treating 1-2 pulmonary metastases in 34 patients with various primary tumors using 12 Gy fractions to doses of 48 or 60 Gy, at 2 years, 90% of patients were free of local failure. (18). Little toxicity has been reported when SBRT is used to treat peripheral lung tumors, with pneumonitis rates varying from 0% to 10% (19-20).

The role of SBRT for liver lesions was evaluated in a pilot study of 31 patients with a variety of primary tumors, 17 liver metastases in 14 patients were treated with doses of 7.7-45 Gy in 1-4 fractions. Of 13 lesions treated with greater than 20 Gy, only one lesion progressed with a mean follow-up of almost 10 months (23). A phase I multi-institutional trial sequentially escalated doses up to 60 Gy in three fractions. It was reported that the maximum tolerated dose (MTD) was not reached and a single patient out of 36 patients failed in-field at a median follow-up of 19 months (24).

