3.1 Conditions for Patient Eligibility

3.1.1 Pathologically (histologically or cytologically) proven diagnosis of solid malignancy within 8 weeks of registration

NOTE: FDG-PET/CT scans are required for full staging of metastatic disease. If subject has had an FDG-PET/CT scan within the last 8 weeks, it will not need to be repeated.

NOTE: Pathological confirmation is not required for all disease sites as long as the sites of metastatic disease are radiographically and clinically consistent with metastatic disease from a known (biopsy proven) primary.

NOTE: the primary site does not have to be the site of pathological confirmation. For example, in a patient with a radiographic lung lesion with mediastinal

lymphadenopathy and a liver lesion, a liver biopsy which is constant with lung primary would preclude the necessity for further pathologic diagnosis.

3.1.2 Eligible disease sites include the following newly diagnosed disease types:

1. Breast
2. Prostate
3. GI (including colorectal, anal, esophagus, pancreas, gastric with the exception of colon cancer with resectable liver-only lesions)
4. Head and neck
5. Skin (melanoma and squamous cell carcinoma)
6. Lung (both small cell and non-small cell)
7. Sarcoma (both soft tissue and bone)
8. Gynecologic (endometrial, cervical, ovarian, vaginal, vulvar)

3.1.3 Patients are stage IV (M1) with any combination of T and N with oligometastatic disease as defined by 5 or fewer total sites of metastatic disease involving 3 or fewer organ systems

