10.3 Evaluation after study

10.3.1 Patients will be seen in follow-up with study physicians 6 weeks after completion of SRS/SBRT and then at 3 month intervals for 3 years and 6 months thereafter.

10.3.2 QOL survey to be performed prior to therapy, after SRS/SBRT and at subsequent follow-up visits using the FACT-G survey. See Appendix IV.

10.3.3 Toxicity will be evaluated after the study using Common Cancer Toxicity Criteria V 4.0

10.3.4 Follow-up imaging should be performed at least every 3 months for the first two years from completion of therapy and every 6 months afterwards until five years from the completion of therapy. FDG-PET/CT scan for follow-up is recommended but not required.

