10.3.5 Measurement of Response for CT scans

Response will be evaluated in this study using the international criteria proposed by the Response Evaluation Criteria in Solid Tumors (RECIST) Committee [JNCI 92(3): 205-216, 2000] See <http://ctep.info.nih.gov/guidelines/recist.html> for further details.

1. Measurable disease - the presence of at least one measurable lesion; if the measurable disease is restricted to a solitary lesion, its neoplastic nature should be confirmed by cytology/histology.
2. Measurable lesions - lesions that can be accurately measured in at least one dimension with longest diameter \geq 20 mm using conventional techniques or \geq 10 mm with spiral CT scan.
3. Non-measurable lesions - all other lesions, including small lesions (longest diameter $<$ 20 mm with conventional techniques or $<$ 10 mm with spiral CT scan), i.e., bone lesions, leptomeningeal disease, ascites, pleural/pericardial effusion, inflammatory breast disease, lymphangitis cutis/pulmonis, cystic lesions, and also abdominal masses that are not confirmed and followed by imaging techniques

Response Criteria: Evaluation of target lesions

*Complete Response (CR): Disappearance of all target lesions

*Partial Response (PR): At least a 30% decrease in the sum of the LD of target lesions, taking as reference the baseline sum LD

*Progressive Disease (PD): At least a 20% increase in the sum of the LD of target lesions, taking as reference the smallest sum LD recorded since the treatment started or the appearance of one or more new lesions

*Stable Disease (SD): Neither sufficient shrinkage to qualify for PR nor sufficient increase to qualify for PD, taking as reference the smallest sum LD since the treatment started

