10.4 Criteria for Discontinuation of Protocol Treatment

- Progression of disease as measured by RECIST criteria outlined above, PET scan RECIST criteria will be used for patients with follow-up PET scans, CT scan RECIST criteria will be used for patients with follow CT scan only.

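### For patients followed by CT only, size-based progression has no minimum mm increase and no stated confirmation, so when the target-lesion sum is small, measurement error alone can be scored as PD

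*Combined protocol and SAP*

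**What the plan says.** Section 10.3.5 takes its CT response criteria from a published standard: "Response will be evaluated in this study using the international criteria proposed by the Response Evaluation Criteria in Solid Tumors (RECIST) Committee". It then writes out the size criterion for progression as "At least a 20% increase in the sum of the LD of target lesions, taking as reference the smallest sum LD recorded" since treatment started. A second route to PD, independent of size, is "or the appearance of one or more new lesions".

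The section gives no minimum absolute increase and says nothing about confirming PD on a later scan. A lesion is measurable at baseline from "10 mm with spiral CT scan", but no lower limit applies to the later readings that set the reference. Bone lesions are listed as non-measurable.

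On timing, section 10.3.4 states: "Follow-up imaging should be performed at least every 3 months for the first two years" from completion of therapy, then every 6 months to five years. Follow-up PET is recommended but optional. Section 10.4 uses "Progression of disease as measured by RECIST criteria outlined above" as the discontinuation criterion and reserves the CT criteria for patients whose follow-up is by CT alone. Patients with follow-up PET are judged by the visual criteria of 10.3.6.

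Section 2.0 makes local control (CR, PR or SD), the proportion with PD and time to failure secondary endpoints.

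**The concern.** A purely relative threshold shrinks with the reference. When the target sum is a centimetre or less, 20% is 2 mm or less, which may be no more than reading error. The reference is also the minimum of repeated readings, so chance pulls it downward, and every further scan is another opportunity to exceed it.

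Small sums are plausible in this trial. Eligibility is "5 or fewer total sites of metastatic disease involving 3 or fewer organ systems", with no lower limit beyond having metastatic disease, and section 7.2 gives a solitary adrenal lesion as an example. The eligible colorectal example in 3.1.3.1 has one liver lesion and four bone lesions. Since bone lesions are non-measurable, its only measurable metastasis is the liver lesion. A good response to SBRT lowers the reference further.

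The bias runs one way. False PD lowers local control, raises the proportion with PD and shortens time to failure, most of all in patients with the least measurable disease. With the 40 patients planned in section 11.2, one false call moves an overall proportion by 1/40 = 2.5 points. In a subset of about 10 it moves it by 1/10 = 10 points.

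**Working it through.** **Inputs from the documents.** Threshold 20% over the smallest sum since treatment started (10.3.5); measurable from 10 mm on spiral CT (10.3.5); scans every 3 months for two years, so 24/3 = 8 follow-up scans (10.3.4). The plan states no error rate for this rule, so there is no figure of its own to reproduce.

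**Assumptions, not from the documents.** Reading error is independent between scans and lesions, with SD 0.5, 1.0 or 1.5 mm per lesion. The floor is 5 mm.

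**Step 1: rise needed.** Rise = 0.20 × smallest sum.

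| Smallest sum (mm) | Rise for PD (mm) |
|---|---|
| 5 | 1 |
| 10 | 2 |
| 20 | 4 |
| 25 | 5 |
| 30 | 6 |
| 60 | 12 |

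A 2 mm rise is PD only if the whole target sum was 10 mm or less; a 1 mm rise only if it was 5 mm or less. With three 20 mm targets, 2 mm is 2/60 = 3.3% and is not PD. A 5 mm floor changes the threshold only below 25 mm, because 0.20 × 25 = 5.

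**Step 2: one comparison.** For one unchanged 10 mm target at SD 1.0, the first follow-up reading X1 is PD if X1 − 1.2·X0 ≥ 0, where X0 is the baseline reading. That difference has mean 10 − 12 = −2 and SD √(1 + 1.44) = 1.56. Since 2/1.56 = 1.28, the chance is about 10%.

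**Step 3: eight comparisons.** Simulation, no true change, baseline plus 8 scans, running minimum as reference, readings unrounded. Confirmation means that the next scan also meets the rule. Chance of at least one PD call for a sole 10 mm target:

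| Rule | SD 0.5 | SD 1.0 | SD 1.5 |
|---|---|---|---|
| As written | 12% | 83% | 97% |
| Plus 5 mm floor | 0% | 0.7% | 19.5% |
| Floor and confirmation | about 0% | 0.02% | 2.3% |

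At SD 1.0, repeated looks against a falling minimum take the chance from about 10% at the first scan to 83% over eight.

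**Step 4: larger sums, as written, SD 1.0, unrounded.**

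| Targets | Ever PD |
|---|---|
| One 20 mm | 12% |
| Two 10 mm | 50% (14% with the floor) |
| 10 + 20 mm | 8% |
| 10 + 30 mm | 0.5% |
| 10 + 40 mm | about 0% |
| Two 20 mm | 0.5% |
| Three 10 mm | 26% (26% with the floor, 4.7% with confirmation) |

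The last row shows the limit of the floor: at a sum of 30 mm it does nothing, and only confirmation helps.

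**Step 5: readings rounded to whole mm.** Sole 10 mm target, SD 0.5 / 1.0 / 1.5:
- as written: 43 / 91 / 98%
- 5 mm floor: 0 / 2.5 / 31%
- confirmation alone: 8 / 53 / 76%
- both: about 0 / 0.1 / 5%

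The ordering is the same. For a very small sum, confirmation alone is not enough. Rounded and unrounded figures should not be compared with each other.

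**The case against.** The strongest reply is about scope, and much of it stands.

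- **The rule acts on a sum.** A reader might infer that any small treated metastasis becomes PD on a 1–2 mm re-measurement. That is true only when the whole target sum is 10 mm or less. Other targets dilute the effect quickly, as Step 4 shows.
- **Not every patient is judged by CT.** PET is recommended in follow-up, and 10.4 sends those patients to the visual criteria. The size of the CT-only group is unknown.
- **The error SDs are assumed.** The headline case is also the smallest lesion that can be a target at baseline.
- **The plan adopts a published standard and refers to it for details.** The text is therefore silent on confirmation; it does not rule it out. An endpoint rule should still be explicit in the protocol.

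Three further inferences are tempting but unsupported:
- That resecting the primary drops the reference sum to the metastases alone. Nothing puts primary and metastases in one sum, and their local control is reported separately.
- That post-SBRT lung changes will be read as growth. Section 1.0 says "toxicity has been mild, most commonly limited to radiographic lung changes", which describes toxicity and not an increase in longest diameter.
- That false calls will cut much protocol treatment short. SRS/SBRT is completed within 3 weeks (6.2.1), and the 3-monthly imaging runs from completion of therapy.

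What survives is narrower: for CT-only patients with a small target sum, the rule as written does not separate growth from reading error.

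**Conclusion.** The concern holds in this limited form. The threshold arithmetic is exact and needs no assumption. The false-call rates depend on the assumed reading error: for an unchanged sole 10 mm target over 8 scans they run from 12% to 97% as SD goes from 0.5 to 1.5 mm. At SD 1.0 they fall to 0.5% or less for two 20 mm targets or for 10 mm plus 30 mm.

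How many patients are exposed cannot be derived. The documents give neither lesion sizes nor the share followed by CT alone, and they do not say how many lesions are targets or whether the primary shares a sum with the metastases. I read the PET/CT split in 10.4 as applying to endpoint scoring as well as to discontinuation.

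The affected results are local control, the proportion with PD and time to failure. The toxicity endpoint and overall survival do not use this definition, and no sample size or power calculation rests on it. The change is worth making because the bias has one direction and the remedy is cheap. It does not threaten the trial's primary objective.

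**What to change.** Add a scoring rule to section 10.3.5 or section 11.3, for example:

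> For scoring local control, the proportion with PD and time to failure, size-based progression on CT requires an increase of at least 20% and at least 5 mm over the smallest target sum since treatment started, still present on the next scheduled scan. Failure is dated to the first of the two scans. The new-lesion criterion is unchanged. This scoring rule does not alter the discontinuation criterion in section 10.4.

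The last sentence is needed because 10.4 refers back to 10.3.5; an unrestricted edit there would also change when treatment is discontinued, which is for the investigators to decide. Both parts of the rule are needed: the floor acts below a sum of 25 mm, and confirmation is the only protection above it. The 5 mm value is a proposal, not a figure from the documents.

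Cost: a few sentences and no extra imaging. Growth of very small lesions is called slightly later. Confirmation takes 3 months in the first two years and 6 months after that. A call on a patient's last scan stays unconfirmed and should be reported as such.

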2.0 OBJECTIVES

Primary objective: Delivery of SBRT to multiple sites in a safe and effective manner with acceptable toxicity

Primary Endpoints:

- Presence of multiple sites (between 2 and 5 sites)
- Acceptable toxicity: Grade 3 or less

Secondary Objectives/Endpoints:

- Quality of life (as measured by the FACT quality of life surveys, see appendix IV)
- Local control of metastatic sites (with measurable/quantitative assessment): proportion of patients with Complete Response (CR), Partial Response (PR), or Stable Disease (SD)
- Local control of primary site (with measurable/quantitative assessment): proportion of patients with local Complete Response (CR), Partial Response (PR), or Stable Disease (SD)
- Overall survival (OS)
- Two-year Overall Survival
- Analysis of patterns of failure post-SRS/SBRT (subsequent sites of failure and time to failure): proportion of patients with Progressive Disease (PD)

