10.3.6 Measurement of Response for FDG-PET scans

Since it is extremely difficult to quantify the size of a lesion(s) by FDG-PET scan, the conventional RECIST criteria will not be used for the qualitative, non-SUV-based FDG-PET scan interpretation after chemoradiotherapy. Instead, the qualitative visual criteria from MacManus et al will be utilized, as follows:

Response Criteria: Evaluation of target lesions

*Complete Response (CR): CR will be defined as no tumor FDG uptake in the tumor bed, or activity in the tumor bed similar to that in the adjacent normal tissue;

Partial Response (PR): appreciable reduction in intensity of tumor FDG uptake or tumor volume apparent to the nuclear medicine physician when pre-, during-, and post-treatment PET scans are displayed side by side;

Progressive Disease (PD): appreciable increase in the intensity of tumor FDG uptake or volume of the tumor apparent to the nuclear medicine physician when pre-, during-, and post-treatment PET scans are displayed side by side.

Stable Disease (SD): no appreciable change in intensity of tumor FDG uptake or tumor volume between scans and no new sites of disease apparent to the nuclear medicine physician when pre-, during-, and post-treatment PET scans are displayed side by side;

** For these determinations, the pre-, during-, and post-treatment FDG-PET scans must be analyzed using the same display techniques to provide a consistent intensity of background soft-tissue activity.*

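### A new lesion is progression on CT but not, by itself, on PET, so the PD proportion depends on scan type; on CT a distant lesion can also count against local control

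*Combined protocol and SAP*

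**What the plan says.** All references are to the combined protocol and SAP.

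**Endpoints (2.0).** Two secondary endpoints are built on response categories: "Local control of metastatic sites (with measurable/quantitative assessment): proportion of patients with Complete Response (CR), Partial Response (PR), or Stable Disease (SD") and "Analysis of patterns of failure post-SRS/SBRT (subsequent sites of failure and time to failure): proportion of patients with Progressive Disease (PD").

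**CT (10.3.5).** PD is a rise of at least 20% in the summed longest diameter of target lesions, "taking as reference the smallest sum LD recorded since the treatment started or the appearance of one or more new lesions". Complete response (CR) is "Disappearance of all target lesions". Partial response (PR) is "At least a 30% decrease in the sum of the LD of target lesions". SD is "Neither sufficient shrinkage to qualify for PR nor sufficient increase to qualify for PD". CR and PR carry no condition on new lesions, and the printed text does not say which category wins when two are met. The section refers to the published RECIST criteria for further details.

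**PET (10.3.6).** CR is "no tumor FDG uptake in the tumor bed, or activity in the tumor bed similar to that in the adjacent normal tissue". PR is a visible reduction in uptake or volume, again with no condition on new sites. PD is "appreciable increase in the intensity of tumor FDG uptake or volume of the tumor apparent to the nuclear medicine physician". SD requires unchanged uptake and volume and also that no new site is seen.

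**Which scan.** Appendix I marks FDG-PET/CT at follow-up, while 10.3.4 recommends it without requiring it. The only rule that assigns criteria by scan type is in 10.4, and it concerns stopping protocol treatment.

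**The concern.** The trial treats a limited set of metastases with SBRT. A reader of its results will want two separate answers: did the treated sites stay controlled, and did disease appear elsewhere? As printed, the categories mix these on CT and leave part of the second unrecorded on PET. Two patients with the same course, controlled treated lesions and one new metastasis, can be classified differently because one had PET and the other CT.

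At stake are the proportion with PD and the proportion with local control of metastatic sites. Section 11.2 plans subsets of about 10 patients partly so that local control can be estimated in each. If scan type differs between subsets, part of an apparent difference between them could come from the scoring rule.

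**Working it through.** **1. Category definitions side by side.** Take a patient with a new lesion and apply the printed wording to each possible state of the target lesions.

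| Target lesions | CT criteria met (10.3.5) | PET criteria met (10.3.6) |
|---|---|---|
| Gone | CR and PD | CR |
| Reduced | PR and PD | PR |
| Unchanged | PD (also SD, if SD is read on size alone) | none |
| Grown | PD | PD |

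The rows are states, not frequencies, and nothing should be counted from them.

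**2. PD proportion.** On CT every row meets PD. On PET only the last row does, and there because the targets grew. In the first two rows the PET patient remains a responder. In the third the patient is in neither the CR/PR/SD proportion nor the PD proportion. If PET is read under 10.3.6 alone, the PD proportion is therefore lower than CT would give for the same patients.

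**3. Local control of metastatic sites.** On CT the answer turns on precedence. If PD overrides, the first three rows are lost from local control although no treated site has progressed. If the target-lesion category stands, the first two rows remain controlled, and the third does so only if SD is read on size alone. On PET the first two rows are controlled and the third is not.

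**4. Size per patient.** Inputs from 11.2: 40 patients, 10% drop-out, about 10 per subset.

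- The plan's total: 40 × 1.10 = 44, as stated. In reverse, 44 × 0.90 = 39.6, about 40 evaluable.
- One reclassified patient overall: 1/40 = 2.5 percentage points.
- One reclassified patient in a planned subset: 1/10 = 10 percentage points.
- In general, k reclassified patients move the overall proportion by k × 2.5 points.

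The value of k depends on how many patients have a new lesion with controlled targets and on how many are followed by PET. The documents give neither, so no total is calculated.

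**The case against.** **Local control may already be a CT endpoint.** Section 2.0 ties it to a measurable or quantitative assessment, while 10.3.6 describes its own PET reading as qualitative. Together these favour the CT size criteria. On that reading the CT/PET conflict in local control disappears. This stands in large part, although 2.0 does not say so outright and section 11.0 repeats the endpoint without the qualifier. It leaves open whether a new lesion on CT is a local failure, and the qualifier is not attached to the PD proportion.

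**PET/CT includes a CT.** Section 10.3.5 adopts RECIST for the study as a whole, and nothing forbids reading the CT component under it for endpoints. This also stands: understatement of PD is conditional on PET being read under 10.3.6 alone. The documents do not say how the CT component is to be read.

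**The cited RECIST source may settle precedence.** It may, so a reader should not infer that the plan has no rule at all. But neither answer cures both endpoints. If PD overrides, a distant lesion counts against local control. If the target-lesion category stands, a new metastasis beside responding targets goes uncounted as PD on CT as well as PET. Nor can that source be relied on to fill the empty PET category, since 10.3.6 sets RECIST aside for that reading.

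**The intent is site-specific.** Section 2.0 separates local control from subsequent sites of failure, and the introduction uses local control of treated lesions. That is probably what was meant. However, the metastatic-site endpoint is defined through categories that do not implement it.

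A reader might also infer that local control is materially biased, or that the trial's main conclusions are at risk. The documents support neither. The endpoints are secondary, 11.3 sets no test or threshold for them, and the primary endpoints, overall survival and the sample size do not use these categories. Sites of failure and time to failure are listed as items in their own right.

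**Conclusion.** The inconsistency is real and worth correcting before these endpoints are scored. It is firmest for the PD proportion: on PET a new site alone is never PD, and with stable targets it leaves the patient unclassified. The resulting understatement relative to CT assumes that follow-up PET is read under 10.3.6 alone.

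For local control the point is narrower. If PD overrides on CT, a distant lesion removes a patient whose treated sites are all controlled. The further CT/PET conflict shrinks or disappears if 2.0 limits scoring to CT size criteria.

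The reach is limited to descriptive secondary endpoints, at 2.5 points per reclassified patient among 40 or 10 points in a subset of 10. The effect on 10.4 is small, because SBRT ends within 3 weeks (6.2.1) and follow-up imaging is timed from completion of therapy (10.3.4). The problem there is mainly a label that calls the PET criteria RECIST.

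**What to change.** 1. **Overall progression.** In 10.3.6 add *or any new site of disease* to the PET definition of PD. State that, for overall progression, PD takes precedence over CR, PR and SD on both scan types.
2. **Local control.** In 2.0 and 10.3, score it on treated lesions only, so that a new lesion elsewhere is never a local failure. State whether scoring is per lesion, with any progressing treated lesion a local failure, or by summed diameter, where shrinkage in one lesion can hide growth in another. For this score drop the no-new-site condition from PET SD, and say whether the qualifier in 2.0 limits scoring to CT size criteria. Report overall progression beside local control.
3. **Label.** In 10.4, refer to the PET criteria in 10.3.6 in place of PET RECIST criteria. This is a wording correction only.

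The cost is text plus slight per-lesion coding of scans already obtained; lesion number and size are already recorded at baseline (4.1). The downside is that removing new lesions from the local-control score can only leave it equal to or higher than under the literal CT rule, so it must not be shown without overall progression. Per-lesion scoring, if chosen, may pull the other way by exposing growth that a sum would mask.
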